Economic Evaluation Supplement Aim: To understand the economic impact of the Southwest Hub interventions. We hypothesize that both the NH and ER interventions' reduction in participant suicidal ideation and improved resilience will reduce participant healthcare and other community and personal costs compared to the standard of care of CM alone.

1. Administer a time use survey (e.g. time-logs) and conduct in-person interviews among the project staff and health workers. Using these tools, we will ask staff to recall how they allocated their time and what resources (e.g. supplies, equipment, etc.) they used.
2. Analyze Celebrating Life Apache surveillance system (CL) data for related data points for study participants, including intake and follow-up case management visits. This data counts the number of times study staff visited or attempted to visit study participants, and is key in accounting for the time and financial costs of conducting study visits with participants.

Diversity Supplement Aim: To assess individual characteristics (age, gender, substance use history, mental health status, educational and employment status, family composition) associated with co-occurrence of suicide ideation or attempts and history of opioid use compared with suicide risks alone

Secondary Aims:

2. To examine mediators and moderators of treatment effectiveness and sequencing in order to determine which types and sequence of interventions is best suited for which youth.
3. To assess the acceptability, feasibility and capacity for sustainability of the Hub's key intervention components (Surveillance/Case Management, New Hope and Elders' Resilience) from the perspective of multiple stakeholders as they are implemented across different tribes. This will also include identifying, prioritizing and testing strategies aimed at enhancing the sustainability of tribally implemented suicide prevention programs.

Opioid Data Collection Sub-Study Aim: Explore community beliefs about: a) correlates of risk (i.e., other substance use, mental health status, family, demographic and social factors), b) protective factors (cultural and spiritual factors) and c) behavior functions (i.e., emotional regulation, reinforcement patterns) of opioid abuse in Native American youth through focus groups with the existing Community Advisory Boards from the Hub partners.

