episode with recent suicidal ideation (i.e., index event); and 2) **implementation of a Sequential Multiple Assignment Randomized Trial (SMART)** to inform how to combine and tailor two brief interventions delivered by paraprofessional community mental health workers (CMHWs), with promising pilot data, to prevent further suicidal thoughts and behavior and promote resilience (and decrease long-term risk both due to suicidal behaviors and substance use including opioids); and 3) evaluate what are the cost savings per study participant with the implementation of the Southwest Hub interventions: *NH, ER, NH and ER*. A secondary aim will be to evaluate the acceptability, feasibility and sustainability of the two brief interventions with other Southwest Hub partners, **including the Navajo, San Carlos Apache, Hualapai, and Cherokee nations**, who will have support from the Administrative Core of the Southwest Hub to implement their own local tribal suicide surveillance systems for community-based identification of at-risk youth.

Background on economic evaluation supplemental aim: Little is known about the cost-effectiveness of mental health interventions for Native Americans. Lack of cost-effectiveness evidence is primarily due to lack of scientific evidence on intervention impact as well as obstacles in quantifying the disability burden for suicide ideation using standard metrics. A recent literature review on the cost-effectiveness of suicide and self-harm prevention interventions shows six studies provided high quality evidence and all six interventions were cost-effective. However, none of these focused on addressing suicidality in Native American populations and none included culturally appropriate interventions for this population. Our partners from the White Mountain Apache Tribe have indicated a strong interest in learning about the economic burden of suicide and costs of addressing it in order to inform policy decisions and future implementation and dissemination of these programs in other tribal settings.

As part of the *economic evaluation supplemental aim* we will administer a time use survey (e.g. time-logs) and conduct in-person interviews to assess the costs of the intervention. The rationale for these activities is doing quality control and capturing all the program resources needed to run the HUB interventions.

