For the economic evaluation supplement, we will use all healthcare claims data for each intervention participant (from one year prior to the study period to 12 months post-enrollment--for a total of 2 years of participant claims data) requested from the Indian health Service's electronic health records to assess healthcare expenditures. We will also ask participants about their school performance and work attendance, as well as, some additional items related to time spent participating in the interventions. These new items for participants are included in the assessment battery.

As part of the economic evaluation supplement, we will collect data from staff about their time use and resources use. For this aim, we will ask all project case managers and health providers to collect daily time-logs. The design of the time-log may vary overtime to better fit program needs or activities. But in general, this tool will ask staff to select which of a pre-defined list of activities they conducted each day and for how many hours each activity. In-person interviews with staff will follow a semi-structure design. A survey tool will be used to guide open ended questions and the survey will be modified over-time to fit program activities.

We will also analyze CL data for related data points for study participants, including intake and follow-up case management visits. This data counts the number of times study staff visited or attempted to visit study participants, and is key in accounting for the time and financial costs of conducting study visits with participants.

For the diversity supplement, we will compare individual characteristics associated with co-occurrence of suicide ideation or attempts and opioid use vs. suicide ideation/attempt without concurrent opioid use risk. We will use

baseline measures of age, gender, mental health status, education, employment, academic status, income, and family composition already being collected by the parent grant.

Aim 2: To examine mediators and moderators of treatment effectiveness and sequencing in order to determine which types and sequence of interventions is best suited for which youth.

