Aim 1: We will randomize **304 participants**; 76 to CM alone, 76 to CM+NH, 76 to CM+ ER, and 76 to CM+NH+ER. Based on the previous work with the SIQ, we believe a 25% reduction among individuals with a score of 30 or greater would represent clinically significant change in suicide ideation.[5] Using pilot data of NH among the WMAT, an average baseline score of 45 could be expected on the SIQ.[5] A clinically significant reduction translates into a large Cohen's D effect size (>0.8). However, we want the power to observe the more moderate effect expected to result from comparing the sequencing of the interventions (NH+ER vs. NH+CM vs. CM+ER vs. CM alone). Using an adjusted alpha to account for multiple comparisons of 0.013, and a correlation of 0.2 among repeated measures, with four groups (NH+ER vs. NH+CM vs. CM+ER vs. CM alone), $n=58$ people per group ($n=116$ randomized at each randomization time-point) would provide 80% power to detect a small to moderate effect (Cohen's $F=0.2$). Adjusting these estimates for 30% attrition would result in $n=76$ per each of the four groups ($n=152$ per arm) for a total sample size of $N=304$.

Please note for our ***the Opioid Data Collection Sub-Study***: We will use a mixed methods approach to examine opioid use among our SMART trial participants through addition of a quantitative opioid related measure and qualitative interviews ($N=30$) with a subset of those who endorse recent or current use.

For the economic evaluation supplement: We will use the same sample of participants as Aim 1. We are not drawing statistical inferences about cost estimates so there is no sample size requirement. Instead, we are reporting on the health care services utilization and costs incurred by study participants before, during and after the intervention. To administer a time use survey and conduct in-person interviews we will use all HUB program case managers (five or more) and healthcare providers (three or more).

For the diversity supplement: We will use a sub-sample of $n=239$ WMAT participants enrolled in the parent trial. This sample size is based on the estimated enrollment rates during the Diversity Supplement study period.

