For the economic evaluation supplement aim: To evaluate healthcare expenditures per participant and intervention we will employ standard two-part regression models used in the analysis of healthcare costs. Variables per claim will include non-identifiable individual study ID, utilization date, charge per claim, and CPT code. Service claims will include all inpatient services and respective length of stay, ED services, outpatient services, specialist care, pharmaceuticals, home health, health transportation, and mental health care utilization and any other health-care related costs. In addition, time use of our staff will be categorized according to the various protocols that they work on. We will estimate the weekly total hours spent in delivering services to youth. The cost of the time allocated to youth services will be estimated by multiplying wage rate for that worker times hours spent delivering services to youth.

We will analyze Celebrating Life Apache surveillance system (CL) data for related data points for study participants, including intake and follow-up case management visits. This data counts the number of times study staff visited or attempted to visit study participants, and is key in accounting for the time and financial costs of conducting study visits with participants.

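### Healthcare expenditure is to be measured by the billed charge on each claim, with no conversion to payment or cost, while staff delivery time is priced at wages

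*Combined protocol and SAP*

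**What the plan says.** Section I (Economic Evaluation Supplement Aim) hypothesises that the effects of New Hope (NH) and Elders' Resilience (ER) "will reduce participant healthcare and other community and personal costs compared to the standard of care of CM alone", where CM is case management. Section II promises to "evaluate what are the cost savings per study participant with the implementation of the Southwest Hub interventions", listing NH, ER, and the two together. Section III.A says that claims will be requested from Indian Health Service (IHS) records "to assess healthcare expenditures".

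The analysis is in Section V.C, item 4: "To evaluate healthcare expenditures per participant and intervention we will employ standard two-part regression models used in the analysis of healthcare costs". The claim fields follow: "Variables per claim will include non-identifiable individual study ID, utilization date, charge per claim, and CPT code". The claims span inpatient, emergency, outpatient, pharmacy and other services.

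The same item values staff time by "multiplying wage rate for that worker times hours spent delivering services to youth". Other delivery inputs are collected as well. Section I says that "we will ask staff to recall how they allocated their time and what resources (e.g. supplies, equipment, etc.) they used", Section V.C, item 2 adds interviews on resources used, and surveillance-system visit counts are to inform visit costs. Only staff time has a stated pricing formula.

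Section III.B adds: "We are not drawing statistical inferences about cost estimates so there is no sample size requirement".

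The documents give no paid or allowed amount, fee schedule, charge-to-cost conversion, costing perspective, price year, or rule for combining the claims part with the delivery part.

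**The concern.** What is billed need not equal what is paid or what the care costs to provide. The plan names expenditure as the outcome and lists only the billed amount to measure it. Followed as written, the two-part models would be fitted to charges and the results reported as expenditures. That mismatch exists even if claims are never set against delivery cost.

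A second question arises if they are combined. Healthcare would then be counted at charges and staff time at wages, and a net figure would depend on the gap between the two price bases. Section II records that the tribal partner wants to learn the economic burden of suicide and the cost of addressing it, to inform policy and dissemination. For that use the dollar amounts matter, not only the direction of a difference.

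**Working it through.** **What can be reproduced.** The documents state no charge, wage, cost or saving, so there is no economic figure to reproduce. The related contact hours do reproduce. Section V.C, item 2 gives visits of 2 + 1 + 1 + 1 + 1 = 6 hours, plus 2–4 hours for NH and 2–4 for ER. The total for both is 6 + 4 = 10 to 6 + 8 = 14 hours, which matches Section VII.D. The extra contact time for NH plus ER is therefore 4–8 hours.

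**Notation.**
- S = reduction in billed charges per participant against CM alone (negative if use rises).
- W = delivery cost per participant.
- r = cost-to-charge ratio. Not in the documents; assumed 0.3 to 1.0.
- For W, an assumed wage of $15–40 per hour gives 4 × 15 = $60 to 8 × 40 = $320 for one worker, without travel, preparation, the Elder, supplies or overheads. W = $300 is used below.
- The values of S are also assumptions.

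**Step 1: healthcare component alone.** The reported difference is S, and on a cost basis it is r × S. The reported size is therefore 1/r times the cost-based size.

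| r | 1/r | cost-based difference when S = $500 |
|---|---|---|
| 0.3 | 3.33 | $150 |
| 0.5 | 2.00 | $250 |
| 0.7 | 1.43 | $350 |
| 1.0 | 1.00 | $500 |

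With one common r, the direction and the ratio between arms do not change; only the dollar amounts scale. If r differs by service type, summing charges across services also changes their relative weights. The documents do not show whether it does.

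**Step 2: a net figure, if one is formed.** On mixed bases the net saving is S − W; on a cost basis it is r × S − W. The difference is (1 − r) × S.

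| S | mixed basis | r = 0.3 | r = 0.5 | r = 0.7 | r = 1.0 |
|---|---|---|---|---|---|
| +$2,000 | +$1,700 | +$300 | +$700 | +$1,100 | +$1,700 |
| +$500 | +$200 | −$150 | −$50 | +$50 | +$200 |
| $0 | −$300 | −$300 | −$300 | −$300 | −$300 |
| −$500 | −$800 | −$450 | −$550 | −$650 | −$800 |

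An apparent net saving becomes a net cost when r < W/S < 1. At S = $500, W/S = 300/500 = 0.6, so the sign flips at r = 0.3 and 0.5 but not at 0.7. At S = $2,000, W/S = 0.15 and no r in the assumed range flips it.

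**Step 3: direction.** For r below 1, (1 − r) × S is positive when use falls, zero when use is unchanged and negative when use rises. A charge reduction therefore overstates the saving, and a charge increase overstates the added cost.

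**The case against.** The tempting stronger reading is that the reported savings will be overstated. The documents do not support it. It needs charges above cost or payment at this payer, for which they give no figure. It also needs lower healthcare use under NH or ER, which Section I only hypothesises. The description of NH in Section V.C says that it helps participants start and keep to treatment, so claims could rise. The same method would then make the interventions look worse than they are.

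A reader might also infer that charges will be netted against wages. The plan does not say so. Section V.C, item 4 introduces staff time as a separate item, and Section III.B speaks of reporting utilisation and costs before, during and after the intervention. If the two parts stay separate, the sign-flip in Step 2 never arises. Nor is delivery costed on wages alone, since supplies, equipment and other resources are collected too.

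Three further points can be made for the plan:
- CPT codes are listed beside the charge and would permit repricing, the field list is not expressly closed, and the form asks only for a brief analysis plan.
- The documents do not say what the IHS charge field represents, or whether a paid amount exists in those records.
- No inference on costs is planned.

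All of this removes any claim about direction and makes the net calculation conditional. It does not remove the mismatch. The plan names expenditure, lists the charge as its only price, and does not say that the CPT codes will be used to reprice. The absence of inference does not help, because a descriptive mean on the wrong price basis is off by the same factor.

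**Conclusion.** The point holds as a mismatch between the stated outcome and the stated variable: billed charges stand where expenditures and savings are claimed, and nothing brings them to the price basis used for staff time. The dollar size of any between-arm healthcare difference is distorted by 1/r. That is 1.43-fold to 3.33-fold for an assumed r of 0.7 to 0.3, and nil at r = 1. The sign of the bias cannot be known from the documents, because it depends on r and on whether use falls or rises. A change of sign in a net figure is possible only if the two parts are combined and r < W/S < 1. Every dollar value and ratio in the working is an illustration. The point bears on the economic supplement only, not on the suicidal ideation or resilience outcomes, and it should be settled before the cost analysis is run.

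**What to change.** In Section V.C, item 4, state the price basis of the dependent variable in the two-part models, in this order of preference:

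1. Use the paid or allowed amount, if the IHS records hold it. Whether they do must be checked with the data holder.
2. Otherwise reprice the claims from the CPT codes already requested, or apply a stated cost-to-charge ratio by service type, with a sensitivity analysis over a low-high range.
3. If neither is possible, label the result as billed charges, report it separately from delivery cost, and do not call it expenditure or savings.

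In the same place, state the costing perspective and price year, say how the non-wage resources collected by interview will be priced, and say whether and how healthcare and delivery costs will be combined.

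The cost is some extra analysis work, possibly one more field in the claims request, and a savings figure that may be less favourable. No change to participant procedures or to the main trial analysis is needed.
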